1. SYNOPSIS

Title: A randomized phase II trial of fulvestrant or exemestane with or without Ribociclib after progression on aromatase inhibition plus cyclin-dependent kinase 4/6 inhibition in patients with unresectable or metastatic hormone receptor positive, HER2 negative breast cancer.

Short Title: Study of efficacy of ribociclib plus fulvestrant or exemestane after progression on CDK4/6 inhibition in patients with HR+ HER2- metastatic breast cancer.

Patient Selection (Section 3 for complete inclusion and exclusion criteria details)

1. Men or women at least 18 years of age with histologically or cytologically confirmed adenocarcinoma of the breast with metastatic **or** unresectable disease.
2. Hormone receptor positive (HR+) status, defined as **either** estrogen receptor positive (ER+), progesterone receptor positive (PgR+), or both, as defined by immunohistochemistry (IHC) $\geq 1\%$ as per the ASCO-CAP guidelines.
3. HER2/ErbB2 negative (HER2-) status as per ASCO-CAP
4. Postmenopausal status **or** receiving ovarian suppression, including GnRH agonists (such as goserelin).
5. Evidence of measurable **or** unmeasurable disease.
6. Stable CNS disease allowed.
7. Eastern Cooperative Group (ECOG) performance status of 0 **or** 1.
8. No evidence of clinically significant congestive heart failure or other serious cardiac disease.
9. Adequate renal, liver, and bone marrow function.
- 10a. Written informed consent and HIPAA authorization obtained from the subject/legal representative prior to performing any protocol-related procedures;
- 10b. Subjects must be willing and able to comply with scheduled visits, treatment schedule, laboratory testing, and other requirements of the study

Study Design: This is a phase II, multi-center, randomized, double-blind, placebo-controlled trial to evaluate fulvestrant (or exemestane) +/- ribociclib in patients with HR+HER2- breast cancer who have previously progressed on aromatase inhibitor (AI: letrozole, arimidex, exemestane), selective estrogen receptor downregulator (SERD): tamoxifen, or fulvestrant plus CDK4/6 inhibitor (palbociclib, ribociclib, or abemaciclib). Progression free survival is the primary endpoint. The trial will determine whether there is clinical benefit to continuing CDK4/6 inhibition beyond progression.

Patients can be screened and registered at two different time points:

Registration Scenario #1: Before receiving any CDK4/6 inhibitor **or**

Scenario #2: At the time of disease progression while being treated with a CDK4/6 inhibitor (ribociclib **or** palbociclib **or** abemaciclib)+ AI, tamoxifen or fulvestrant

In scenario #1, the study will provide patients with ribociclib + letrozole, but patients will not be randomized until they demonstrate objective evidence of disease progression on treatment. If the patient has previously received letrozole, an alternative AI can be prescribed but will not be provided by the study, i.e. administered as standard of care (ribociclib and letrozole will still be provided by the study). Patients are allowed to have received 4 consecutive weeks of an aromatase inhibitor prior to protocol registration for scenario 1. In scenario #2, patients will be randomized after registration.

At randomization, patients will be assigned to one of the two arms in a 1:1 ratio: 1) Fulvestrant (or exemestane) + ribociclib **or** 2) Fulvestrant (or exemestane) + placebo. Fulvestrant will be given as a 500 mg dose intramuscularly (IM) every 2 weeks for 3 times (loading dose) and then every 4 weeks, as per standard of care. Exemestane will be given as 25 mg orally daily, as per standard of care. The investigational drug ribociclib will be given as 600 mg daily, 3 weeks on/1 week off. Placebo will be administered on the same schedule. For all patients, ribociclib/placebo will be supplied by the study. Fulvestrant or exemestane will be given, as standard of care.

If patient received prior fulvestrant, exemestane must be the hormone therapy backbone in the randomization. If patient received prior exemestane, fulvestrant must be the hormone therapy backbone in the randomization. If neither has been administered, selection of fulvestrant or exemestane in the randomization will be per investigator discretion.

Accrual Target: N= 120 randomized, evaluable patients. Patients will be accrued from 11 academic medical centers in the US, with a goal of completing accrual in two years.

We will ensure that neither registration scenario contains > 60% (N=80) of total study accrual.

Patients will receive treatment on study until disease progression, unacceptable toxicity, or death or withdrawal from study based on patient choice or treating physician's discretion. Every effort will be made to follow patients for primary and secondary outcomes regardless of treatment discontinuation for any reason. Crossover is not built into the study.

Evaluations

Safety Assessment:

History, physical exam, and routine blood work such as blood counts and comprehensive metabolic panel will be performed on day 1 of each treatment cycle, including prior to randomization in patients registered under scenario #1. (i.e. at least every 4 weeks- Section 10: Study Calendar.)

Primary and Secondary Endpoint Evaluations:

[figure not shown]
CT scans of the chest, abdomen, and pelvis and bone scan are to be performed prior to every third cycle of treatment (approximately every 12 weeks, depending on potential treatment delays), and prior to randomization in patients registered under scenario #1. PET scans can substitute for CT scans + bone scan, at the discretion of the onsite investigator. Additional off-schedule scans may be performed if concern for interval disease progression or other disease/treatment related complications. Disease progression will be determined at the local institution, per RECIST 1.1 criteria.

Skin color photography (if skin lesions are present) is recommended every 12 weeks (+/- 1 week) to assess for disease progression or response, particularly in patients with no measurable disease by radiologic criteria. (Appendix I).

Biomarker Assessment:

- 1) Archived tissue from primary and/or metastatic tissue is required, unless not available. If patient is amenable and has accessible tumor, repeat biopsy is optional. These biopsies should be considered in patients with accessible disease. Biopsies can be within 7 days of the cycle (+/- 7 days). Optional biopsies for tissue biomarker assessment will be performed in consenting patients prior to study treatment, at time of initial progression in patients registered under scenario#1, and when the patient goes off study.
- 2) Serum, plasma, and whole blood will be collected at multiple time points (Section 10: Study Calendar) and stored for future biomarker driven studies.

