1.2 OBJECTIVES

1.2.1 Primary Objectives:

1. To evaluate the progression-free survival (PFS) of fulvestrant or exemestane with or without ribociclib after progression on anti-estrogen therapy plus cyclin-dependent kinase 4/6 inhibitor in patients with hormone receptor positive (HR+), HER2- breast cancer.

- **Endpoint: PFS.** Defined as the interval from time of randomization until objective disease progression (local assessment) or death from any cause. Kaplan-Meier estimates will be used to calculate medians and 95% confidence intervals for PFS. A one-sided log-rank test will be used to test for a difference in PFS between the two arms.

1.2.2 Secondary/Exploratory Objectives:

1. To assess the Overall Response Rate (ORR = complete + partial response rate) and Clinical Benefit Rate (CBR= ORR + stable disease rate at ≥ 24 weeks of follow up) in the study population in both arms of the trial, post-randomization.

- **Endpoints: ORR, CBR.** Evaluation of disease will be made according to RECIST criteria (version 1.1) in patients with measurable disease. As this study will enroll patients with measurable and un-measurable disease as defined by RECIST v1.1, ORR will only be assessed in evaluable patients. CBR will also be determined. Patients with non-measurable disease only can be categorized as ‘complete response’, ‘non-complete response’, ‘non-progressive disease’, or ‘progressive disease’, but are sometimes not evaluable. (Section 11.1.4.2: Evaluation of Non-Target Lesions).
 - **Duration of overall response:** The duration of overall response is measured as the time interval from when measurement criteria are met for complete or partial response (whichever is first recorded) until the first date that recurrent or progressive disease is objectively documented
2. For patients in registration scenario #1, to assess the PFS, ORR, CBR, and safety of ribociclib with an aromatase inhibitor in patients with metastatic or unresectable HR+ HER2- breast cancer. This analysis will be based on data collected in the pre-randomization component of the trial for patients registered under scenario #1. There is no comparator arm for this component of the trial, but it will add to the available clinical safety and efficacy data with ribociclib + AI in this population.

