7.3 Ribociclib / Placebo

Management of severe or intolerable adverse reactions requires dose reduction, temporary interruption, and/or discontinuation of ribociclib therapy. Refer to the table below for guidance.

Dose modification guidelines: Dosing Levels

	Ribociclib/Placebo	
	Dose	Number of capsules/tablets & strength
Starting dose	600 mg	3 x 200 mg capsules/tablets
First dose reduction	400 mg	2 x 200 mg capsules/tablets
Second dose reduction	200 mg	1 x 200 mg capsules/tablets

Recommendations for dose reduction, interruption or discontinuation of ribociclib/placebo in the management of specific adverse reactions are summarized in the tables below. Definitions of grading of each Adverse Event are based on CTCAE 4.0. Clinical judgment of the treating physician should guide the management plan of each patient based on individual benefit/risk assessment.

If ribociclib is held, the cycle continues, as the patient will be taking hormone therapy. Missed doses of ribociclib will not be made up.

Subjects enrolled on Scenario 1a who are not able to tolerate ribociclib, despite dose reduction to the lowest dose (200 mg), will come off study and not be randomized to Scenario 1b.

Dose modification for hematologic adverse reactions:

LAB ABNORMALITY /	GRADE	DOSE ADJUSTMENT /
-------------------	-------	-------------------

TOXICITY		MANAGEMENT REC'S
Thrombocytopenia	Grade 1: ($\geq 75 \times 10^9/L$)	No dose adjustment required.
	Grade 2: ($\geq 50-75 \times 10^9/L$)	Dose interruption until recovery to grade ≤ 1 . Re-initiate ribociclib/placebo at the same dose.
	Grade 3: ($\geq 25-50 \times 10^9/L$)	Dose interruption until recovery to grade ≤ 1 . Re-initiate ribociclib/placebo at the same dose level. If grade 3 toxicity recurs, interrupt dose until recovery to grade ≤ 1 and then resume at next lower dose level.
	Grade 4: ($< 25 \times 10^9/L$)	Dose interruption until recovery to grade ≤ 1 . Re-initiate ribociclib/placebo at the next lower dose level. If toxicity recurs at grade 4: discontinue ribociclib/placebo.
Absolute Neutrophil Count*	Grade 1: ($\geq 1.5 \times 10^9/L$)	No dose adjustment required.
	Grade 2: ($\geq 1.0 - < 1.5 \times 10^9/L$)	No dose adjustment required.

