***** Please see Appendix F for Guidelines for Affiliate Institutions for Registration and Data Reporting Requirements.**

13. STATISTICAL CONSIDERATIONS

13.1 Study Design/Primary Endpoint (Sample Size: N=120 randomized evaluable patients)

This is a multi-center phase II, randomized, double-blinded, placebo-controlled trial to evaluate the efficacy of fulvestrant (or exemestane) with or without ribociclib in patients who have previously progressed on an aromatase inhibitor (preferably letrozole) plus CDK4/6 inhibitor (ribociclib or palbociclib or abemaciclib).

Primary Endpoint

The primary endpoint is progression free survival, defined as the time from randomization to the development of progressive disease or death.

Disease status will be assessed with comprehensive radiographic studies every three treatment cycles (approximately every 12 weeks (+/- 1 week), but the development of new signs or symptoms of disease in between scheduled evaluations may prompt off-schedule radiographic or non-radiographic evaluations. Disease status will be assessed based on RECIST 1.1 criteria for measurable (target) and non-measurable (non-target) disease, as outlined in detail in Section 11.

Secondary Endpoints:

All secondary endpoints, including overall response rate (complete response + partial response rates), clinical benefit rate (overall response rate + stable disease rate), overall survival, duration of response, adverse event rate, and biomarker assessment are exploratory in nature. In addition, patients registered under scenario #1 will be assessed for progression free survival, overall response rate, clinical benefit rate, and safety while receiving ribociclib with an aromatase inhibitor (pre-randomization). As there is no comparator arm for this pre-randomization part of the study, further statistical analyses on these will not be possible.

Response rates will be estimated as the proportion of enrolled patients who achieve response, as defined in Section 11. Patients who are lost to follow-up without a valid response assessment will be classified as non-responders.

Statistical analysis:

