Progression-free survival will be estimated by Kaplan-Meier method and group differences between groups will be assessed using log-rank tests. Sensitivity analyses for PFS will be performed taking into consideration, but not limited to imputation of incomplete lesion measurements and study discontinuation due to progression/relapse, drug toxicity or death. Missing data patterns will be examined by summarizing the number of subjects randomized but not treated, the number of subjects who discontinued prematurely and the corresponding factors for early discontinuation. Given the potential the interval between two consecutive assessments may be longer in one arm, leading to an erroneous conclusion about differences between groups, we will perform an additional analysis (i.e. generalized log-rank) with interval censoring, especially if there is a difference in assessment schedules and considerable missing data.

Summary statistics will be calculated to describe the sample characteristics in each group. The distribution of patient responses (as defined by RECIST criteria) will be described using percentages % (n). Continuous outcomes will be summarized using mean \pm SD (standard deviation) or median (interquartile range) for non-normal data. Group comparisons will be evaluated using chi-squared or Fisher's Exact tests for categorical data and two-sided t-tests or ANOVA for continuous outcomes.

Analyses for of primary and secondary outcomes will be based on intention to treat principle, with the exception of safety endpoints, which will only be assessed in patients who receive at least one dose of treatment on study.

Subject to sample size limitations, subgroup analyses for subjects randomized to fulvestrant versus exemestane will also be considered.

All statistical analyses will be performed using SAS (version 9.4, SAS Institute Inc., Cary, North Carolina) with a type I error set at 0.05.

Sample Size Justification:

Assuming a median PFS of 3.8 months with fulvestrant alone upon progression⁸³, we predict that the addition of ribociclib to fulvestrant will lead to a median PFS of at least 6.5 months. Based upon the Evaluation of Faslodex versus Exemestane Clinical Trial (EFFECT), a randomized, double-blind, placebo-controlled, phase III trial of fulvestrant versus exemestane in patients who progressed on prior non-steroidal aromatase inhibition, the median time to progression was 3.7 months in each arm (HR=0.96, 95% CI 0.82

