to 1.13, $p=0.65$). Thus, this new protocol amendment allows subject to be randomized to either fulvestrant or exemestane +/- ribociclib⁶⁹, without an impact on the study design and power. A one-sided log-rank test with an overall sample size of $N=120$ randomized and evaluable subjects and with the significance level alpha set at 2.5%, achieves 80% power to detect an effect size (difference in PFS) of 3 months. We will accrue approximately 150 patients to allow for a 20% drop-out rate, non-evaluable and non-randomized subjects.

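### Imaging is tied to treatment cycles under conflicting rules, not to randomization; if slippage differed by arm, the primary one-sided log-rank test would exceed its 2.5% level

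*Combined protocol and SAP*

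**What the plan says.** PFS runs from randomization (Sections 1.2.1, 11.1.6 and 13.1), and progression is assessed locally by RECIST 1.1. The timing of the scans is described in several places that do not agree.

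- **Synopsis, endpoint evaluations:** before every third cycle, "approximately every 12 weeks, depending on potential treatment delays".
- **Section 13.1, Primary Endpoint:** "Disease status will be assessed with comprehensive radiographic studies every three treatment cycles", glossed as about 12 weeks ±1 week. Off-schedule evaluation is allowed on new signs or symptoms.
- **Section 11.1:** every 3 cycles, about 12 weeks of treatment, ±7 days.
- **Sections 10.1 and 10.2, footnotes:** scans are counted in cycles, preferably within 7 days of Day 1 but allowed up to 14. Each Day 1 is due 28±4 days after the previous Day 1.
- **Section 7.3:** "If ribociclib is held, the cycle continues, as the patient will be taking hormone therapy".
- **Section 6.3, Radiation Therapy:** study treatment is withheld during palliative radiotherapy; no scan rule is given.
- **Section 6.5.1:** patients who stop without radiographic progression go on being scanned, but no interval is given. The 12-weekly follow-up in the calendars is for survival.

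The primary analysis is fixed in Section 1.2.1: "A one-sided log-rank test will be used to test for a difference in PFS between the two arms". Section 13.1 names the hazard, that "the interval between two consecutive assessments may be longer in one arm, leading to an erroneous conclusion about differences between groups". It answers with an additional interval-censored generalized log-rank test, stressed for the case of differing schedules and considerable missing data.

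**The concern.** Progression found on imaging is dated when it is seen. If scans in one arm come systematically later, that arm's PFS times lengthen even when the disease behaves the same in both. The ordinary log-rank test cannot tell this from a treatment effect. It is sensitive here because scans are far apart relative to the expected PFS: with a 3.8-month median, about 40% of patients have progressed by the first scan at 12 weeks (2.76 months, S = 0.60). A small shift of that one scan in one arm therefore reorders a large block of events.

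A schedule that follows treatment leaves this open, because treatment can be interrupted for reasons related to the arm. A schedule that follows the calendar from randomization closes it. The present text contains elements of both, so sites may reasonably follow different rules.

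**Working it through.** **1. The plan's own figure.** Inputs from Section 13.1: "Assuming a median PFS of 3.8 months with fulvestrant alone upon progression", 6.5 months with ribociclib, N = 120, and "with the significance level alpha set at 2.5%, achieves 80% power to detect an effect size (difference in PFS) of 3 months". Under exponential PFS, HR = 3.8/6.5 = 0.585. Events for 80% power (Schoenfeld) = 4(1.960 + 0.842)²/(ln 0.585)² = 109; Freedman's formula gives 115. If all 120 patients have events, power is 83.7% (Schoenfeld) or 81.9% (Freedman). Accrual is 120/0.80 = 150. The stated 80% reproduces, and nothing below changes N, events or alpha.

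**2. The timing rules side by side.** Counting from Cycle 1 Day 1, Cycle 4 Day 1 is nominally day 3 × 28 = 84.

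- Sections 11.1 and 13.1 (±7 days): day 77 to 91.
- Calendars: Day 1 may drift by 3 × 4 = 12 days, so Cycle 4 Day 1 can fall on day 72 to 96 with every visit in window. That is up to 5 days beyond day 91, before the 14-day scan allowance is considered.
- Each Day 1 is counted from the one before, so drift accumulates: 6 × 4 = 24 days by Cycle 7.

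No deviation is needed for scans to leave the window in Section 13.1.

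**3. What unequal slip would do.** Null simulation: 60 patients per arm, exponential PFS with a 3.8-month median in both arms, scans every 84 days with ±7-day scatter, extra slip in the ribociclib arm only, and one-sided rejection at 2.5%. Progression is dated at the first scan after the true event; in the off-schedule columns the stated share is dated at its true time. Slip sizes and off-schedule shares are **assumptions**, because the documents give neither. Entries are rejection rates, with the spread over repeated runs.

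| Ribociclib patients affected, slip per 12-week interval | All scan-detected | 30% off-schedule | 50% off-schedule |
|---|---|---|---|
| None | 2.5–2.7% | 2.5–2.9% | not run |
| 30% of patients, 1 week | 4.7–5.6% | 3.6–4.3% | 2.8% |
| 50% of patients, 1 week | 6.3–7.7% | 4.4–5.2% | 3.9% |
| 50% of patients, 2 weeks | 5.1–6.7% | 4.2–4.8% | 3.5% |
| All patients, 1 week | 14.4–15.7% | 7.2–8.5% | 4.6% |

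Monte Carlo error is 1.96√(p(1−p)/n). With 2,000 runs it is about ±0.7 points at 2.5%, ±1.0 at 5% and ±1.6 at 15%, so neighbouring cells should not be ranked. The rates need not rise steadily with slip, because scans cluster in time.

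**4. The planned additional test.** Here slip is applied to a share of intervals, so every ribociclib patient is exposed and no placebo patient is (2,000 runs per row).

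| Slip | Log-rank | Interval-censored test | Log-rank, 30% off-schedule |
|---|---|---|---|
| None | 2.6% | 2.6% | 2.9% |
| 0.5 week, all intervals | 12.7% | 6.0% | 7.0% |
| 1 week, half | 11.4% | 5.3% | 6.7% |
| 1 week, all | 15.2% | 4.9% | 7.5% |
| 2 weeks, a quarter | 7.1% | 4.3% | 4.7% |
| 2 weeks, half | 9.1% | 3.7% | 6.8% |
| 2 weeks, all | 12.3% | 2.9% | 6.8% |

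The interval-censored test removes most of the excess but not always all of it. With equal schedules both tests are at nominal level.

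**The case against.** A reader might infer that ribociclib's toxicity will cause more dose holds, that holds will delay scans, and that the primary test is therefore inflated. The documents do not support that chain. Section 7.3 says the cycle continues during a hold, and missed doses are not made up, so the most obvious arm-related delay does not by rule move the scan. The trial was double-blind with the same hold rules for ribociclib and placebo. The remaining routes (late Day 1 visits, radiotherapy breaks, scanning after discontinuation) are not shown to differ by arm, and equal slip in both arms does not inflate the error.

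Three further points have force.

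- Section 13.1 already says the interval-censored analysis will be done; the clause after it can be read as emphasis, not as a condition.
- Off-schedule scans are allowed and deaths have exact dates, so the all-scan-detected column is the upper end.
- In this version Scenario 1 is closed. Placebo expired in August 2023 and on-treatment Scenario 2 patients were unblinded (Section 13.6). Patients continuing after that need not follow the study calendar (Sections 6.6 and 10.3), so a new schedule reaches few future scans.

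A reader might also infer that the reported medians cannot be compared with 3.8 and 6.5 months because of the 12-week grid. That does not follow. The 3.8 months is itself the observed median in the fulvestrant-alone arm of the cited phase III trial (Section 2.3), and that trial's scan interval is not in the documents.

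What stands is that the synopsis still lets scans move with treatment delays, the windows conflict, two situations have no scan interval, and the ordinary log-rank remains primary.

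**Conclusion.** The concern holds as an inconsistency with a conditional consequence, not as a demonstrated bias. The imaging rules contradict one another and are anchored to treatment cycles. **If** slippage differed by arm with ribociclib scanned later, the primary test would run above 2.5%. Moderate assumptions put it in single figures. Rates of about 11% or more appear only when slip affects the whole ribociclib arm, spares the whole placebo arm and no progression is found off-schedule.

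These figures rest on exponential PFS and on assumed slip and off-schedule shares. They are a range, not an estimate for this trial; actual scan dates by arm would settle which part of it applies. The change is a cheap improvement that costs no power and leaves the design untouched.

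**What to change.** 1. **One imaging rule.** Reconcile the Synopsis and Sections 6.3, 6.5.1, 10.1, 10.2, 11.1 and 13.1: post-randomization imaging is due every 12 weeks (±1 week) from the date of randomization, regardless of dose holds, cycle delays or treatment discontinuation. Remove the reference to treatment delays and the 14-day allowance.
2. **Unconditional sensitivity analysis.** In Section 13.1, delete the qualifying clause so that the interval-censored generalized log-rank test is always reported beside the primary result.
3. **Show the intervals.** Tabulate actual scan intervals by arm, so readers can see whether the schedules differed.

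Items 2 and 3 apply in full to data already collected and matter most now; item 1 can affect only scans still to come. The cost is protocol wording and one table, with planned scan frequency, N and alpha unchanged. The drawback is that some scans will not coincide with a Day 1 visit.
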